#### 2.2 Endpoints

2.2.1. Primary endpoints

Incidence of adverse events (AEs) and serious adverse events (SAEs)

- 2.2.2. Secondary endpoints
  - Changes from baseline to applicable post-dosing visits in vital signs, physical examination, body weight, EKG and laboratory examination results. Baseline will be the value of measurement closest to and before start of IP administration.
  - 2. Pharmacokinetic parameters of marker ingredient in Careseng 1370, 20(S)protopanaxadiol (PPD) and its metabolites
- 2.2.3. Exploratory endpoints

Exploratory endpoints in item 1 below are measured to explore the immunity

1. Change in lymphocyte activity (based on CD3, CD4, CD8, CD19, CD16 and CD56 assessments, presented as CD3+, CD3+/CD4+, CD3+/CD8+, CD19+, CD16+/CD56+, and CD4/CD8 ratio) on Day2, Day 6 and Day 22 compared to the baseline

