# of sachets of study drug actually administered Total # of sachets of study drug assigned at that level × 100%

#### 6. STUDY MEASUREMENTS

#### 6.1 Eligibility

Eligibility should be thoroughly checked by the investigators at Screening visit and Day 1 visit.

If a volunteer is a screen failure, a minimal set of screen failure information is required to ensure transparent reporting of screen failure subjects, to meet the regulatory authority requirement and to respond to queries from regulatory authorities and IRBs/IECs. Minimal information includes demographics, screen failure details, concomitant medication, and any serious adverse event.

Re-screening for volunteer's eligibility will be allowed if the volunteer is willing to participate in the study and one of the following conditions meets:

- If a volunteer consents to participate and meets the eligibility criteria but a delay occurs in starting to participate in due to certain change in situation such that some measurement relevant to eligibility became invalid owing to the delay
- If the cause of screen failure has now resolved or adequately treated such that volunteer's conditions have now stabilized
- If there is an alternative manner to indicate that the volunteer may be suitable.

In these situations,

- A new eCRF will be used
- A new Screening number will be assigned to the person
- The person will be marked as having been re-screened on both the eCRF and the source document.
- The old eCRF will be completed as fully as possible following eCRF completion guide and data on the old eCRF is not copied to the new eCRF.
- The volunteer needs to sign a new ICF as part of the screening procedure.

It is not appropriate to re-screen a volunteer if he/she has previously failed to meet the eligibility criteria and no further changes or treatments have been able to indicate that the volunteer may be suitable.

Volunteer may be re-tested/measured for procedures relevant to causes of screen failure if investigator considers such causes can be resolved soon.

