#### Screening (Days -14 to -1; Visit 1)

- Obtain informed consent form
- Assign volunteer identifier
- Obtain medical history
- Collect volunteer demographics data
- Record medication history (including concomitant medications)
- Measure height
- Measure body weight
- Perform physical examination
- Assess vital signs
- Conduct 12-lead EKG (test performed within 14 days are acceptable)
- Perform pregnancy (urine or serum test for female volunteers of childbearing potential)
- Conduct laboratory tests (with immunology test) (test performed within 14 days are acceptable) (fasting)
- Conduct chest X-ray (test performed within 14 days are acceptable)
- Assess the volunteer's eligibility for the study (inclusion/exclusion criteria)
- Record adverse events
- Dispense diary

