#### Pre-dose (fasting)

- Measure body weight
- Perform physical examination
- Assess vital signs
- Conduct 12-lead EKG
- Pre-dose PK blood sampling
- Diary return and dispensing
- Assess the volunteer's eligibility for the study (inclusion/exclusion criteria)

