14.3 SAFETY DATA

Visit 11 is final visit or early withdrawal visit.

Safety data below except for visit 8 and visit 9 not in its visit window will be shifted to corresponding scheduled visit for analysis as in table below. If there is any data shifting, visit name will be presented as 'Adjusted Visit' for the visits reallocated to its original scheduled visit or the next visit after preceding scheduled visit.

Adjusted Visit	Laboratory Assessment†	Physical Examination	Body Weight	Vital Signs	12-Lead Electrocardiogram
Baseline	N Baseline is Visit 1 (Screening), no need to present statistics for Baseline additionally	N.	Y Baseline is Day 1, or alternatively as Visit 1 if Day 1 data are not available.	Y Baseline is Day 1 Pre-dose, or alternatively as Visit 1 if Day 1 Pre-dose data are not available.	Y Baseline is Day 1 Predose, or alternatively as Visit 1 if Day 1 Predose data are not available.
• Visit 1	Y	Y	Y	Y	Y
• Visit 2 (Day 1)	Y (8 hours post-first dose)	Y (Pre-dose), (8 hours post- first dose)	Y	Y (Pre-dose), (1 hour post-first dose), (4 hours post-first dose), (8 hours post-first dose)	Y (Pre-dose), (1 hour post-first dose), (4 hours post-first dose), (8 hours post-first dose), (12 hours post-first dose)
• Visit 3 (Day 2)	Y	Y	Y	Y	Y (Pre-dose), (1 hour post-first dosing post-first dosing)
• Visit 4 (Day 3)	Y	Y	Y	Y	Y (Pre-dose), (1 hour post-first dosing)
• Visit 5 (Day 4)	Y	Y	Y	Y	Y (Pre-dose), (1 hour post-first dosing)
• Visit 6 (Day 5)	Y (Pre-dose), (4 hours post dosing)	Y (Pre-dose), (4 hours post dosing)	Y	Y (Pre-dose), (4 hours post dosing)	Y (Pre-dose), (1 hour post-first dose), (4 hours post-first dose), (8 hours post-first dose), (12 hours post-first dose)
• Visit 7 (Day 6)	Y	Y	Y	Y	Y
• Visit 8 (Day 7)	N	N	N	N	N
• Visit 9 (Day 8)	N	N	N	N	N
• Visit 10 (Day 12)	Y	Y	Y	Y	Y
• Visit 11 (Day 22)	Y	Y	Y	Y	Y

Y denotes that the Visit is performed in the corresponding tables.

N denotes that the Visit is not performed in the corresponding tables.

[†] Visit 1, 3, 7, 11 only for immunology

Careseng 1370 for Healthy Volunteers

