14.3.5 Laboratory Examination – Immunology

- 14.3.5.1 Immunology CD3 <Unit>
- 14.3.5.2 Immunology CD4 <Unit>
- 14.3.5.3 Immunology CD8 < Unit>
- 14.3.5.4 **Immunology CD16 < Unit >**
- 14.3.5.5 **Immunology CD19 < Unit >**

Version 1.0, 08-SEP-2022 Protocol No.: Careseng 1370-01

Careseng 1370 for Healthy Volunteers

<For continuous Laboratory Examination >

Population: Intent-to-Treat Population

opulation: Intent-to-Treat I opulation	
Characteristics	Dose Level
. (Adjusted) Visits, see visit table below 14.3	
n (Missing)	XXX (XXX)
Mean (SD)	XXX (XXX)
Median (IQR)	XXX (XXX)
Q1~Q3	XXX~XXX
Min~Max	XXX~XXX
n (Missing)	XXX (XXX)
Normal	XXX (XX.X%)
NCS	XXX (XX.X%)
CS (Medical History)	XXX (XX.X%)
CS (Adverse Event)	XXX (XX.X%)
. (Adjusted) Visits - Baseline, see visit table below	
n (Missing)	XXX (XXX)
Mean (SD)	XXX (XXX)
Median (IQR)	XXX (XXX)
Q1~Q3	XXX~XXX
Min~Max	XXX~XXX
95% CI (WI)	XXX~XXXwt
. Baseline to (Adjusted) Visits, see visit table belo	pw 14.3
n (Missing)	XXX (XXX)
Relieved	XXX (XX.X%)
Unchanged	XXX (XX.X%)
Worsened (Medical History)	XXX (XX.X%)
Worsened (Adverse Event)	XXX (XX.X%)

- For CI (WI, within group), t denotes by using one sample t-test, w denotes CI of median (determined by Shapiro-Wilk normality test)
- Refer to [Instructions and Abbreviations] of title pages for Transition of Clinical Relevance

Programmer's Notes:

Present 'Baseline' as Visit 1 (Screening).

Careseng 1370 for Healthy Volunteers

For categorical urinalysis data>Population: Intent-to-Treat Population

Population: Intent-to-Treat Population		
Characteristics	Dose Level	
. (Adjusted) Visits, see visit table below 14.3		
n (Missing)	XXX (XXX)	
<value 1=""></value>	XXX (XX.X%)	
<value 2=""></value>	XXX (XX.X%)	
<value 3=""></value>	XXX (XX.X%)	
n (Missing)	XXX (XXX)	
Normal	XXX (XX.X%)	
NCS	XXX (XX.X%)	
CS (Medical History)	XXX (XX.X%)	
CS (Adverse Event)	XXX (XX.X%)	
Baseline to (Adjusted) Visits, see visit table below	14.3	
n (Missing)	XXX (XXX)	
<value 1=""></value>	XXX (XX.X%)	
<value 2=""></value>	XXX (XX.X%)	
<value 3=""></value>	XXX (XX.X%)	
Baseline to (Adjusted) Visits, see visit table below	14.3	
n (Missing)	XXX (XXX)	
Relieved	XXX (XX.X%)	
Unchanged	XXX (XX.X%)	
Worsened (Medical History)	XXX (XX.X%)	
Worsened (Adverse Event)	XXX (XX.X%)	
,	,	

Refer to [Instructions and Abbreviations] of title pages for Transition of Clinical Relevance

Programmer's Notes:

Present 'Baseline' as Visit 1 (Screening).

Careseng 1370 for Healthy Volunteers

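### The SAP ties laboratory baseline to Screening, so a later pre-dose repeat not filed under Visit 1 would be passed over, against the protocol's rule

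*SAP*

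**What the plan says.** Protocol 2.2.2 makes change from baseline in laboratory results part of the first secondary endpoint and defines the reference value by timing: "Baseline will be the value of measurement closest to and before start of IP administration". Protocol 2.2.3 also compares the lymphocyte markers with baseline.

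The SAP names a visit instead. The laboratory column of the visit table in SAP 14.3 reads "Baseline is Visit 1 (Screening), no need to present statistics for Baseline additionally", and the programmer's notes under the laboratory table shells in 14.3.5 repeat the instruction. The same table treats vital signs differently: "Baseline is Day 1 Pre-dose, or alternatively as Visit 1 if Day 1 Pre-dose data are not available". EKG and body weight follow that pattern.

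Section 1 of the SAP says that it follows protocol version 5.0 apart from the exceptions and clarifications it lists. Sections 1.1 to 1.4 list no change to baseline.

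Protocol 6.1 permits repeat testing before enrolment: "Volunteer may be re-tested/measured for procedures relevant to causes of screen failure", if the investigator expects the cause to resolve soon. Protocol section 7 also allows unscheduled visits, with content left to the investigator.

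**The concern.** A rule based on timing and a rule based on a visit label can select different values. A laboratory test is repeated before dosing because the first result stood in the way of enrolment. If the repeat is acceptable, the volunteer is dosed on the strength of it. The protocol then takes the repeat as baseline, while the SAP as worded keeps the result that it replaced. That result was picked out for being unusual, so later values would tend to look like a return towards normal whatever the drug does.

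At stake are the numeric change summaries, their confidence intervals and the transition tables for hematology, coagulation, biochemistry, urinalysis and immunology. Protocol 1.3 names prolonged PT and APTT in rats as a possible risk, so these tables will be read with some care. Cohorts are small, and one wrong reference value is visible.

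**Working it through.** **1. Age of the Screening sample.** Protocol section 7 places Visit 1 on Days -14 to -1. The SAP listing instructions compute a pre-dose day as the assessment date minus the first treatment date, and the first dosing day is Day 1. A Day -14 sample is therefore 14 days old at first dose and a Day -1 sample 1 day old. The gap is 1 to 14 days. The protocol also accepts Screening laboratory tests performed within 14 days without giving the reference date. If that is counted back from the Screening visit (an assumption), the gap could reach 14 + 14 = 28 days.

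**2. Scheduled pre-dose laboratory values** (protocol section 7).

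| Time point | Laboratory tests | PK blood |
|---|---|---|
| Screening | Yes, with immunology | No |
| Day -1 | No | No |
| Day 1 pre-dose | No | Yes |
| Day 1, 8 hours after first dose | Yes, without immunology | No |
| Days 2 to 5 pre-dose | Yes (immunology on Day 2 only) | Yes |

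Exactly one scheduled laboratory time point precedes the first dose. On scheduled data the protocol's rule and the SAP's label give the same value.

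**3. Where they part.** A later pre-dose result can arise from a re-test (protocol 6.1) or an unscheduled visit. The SAP visit list gives unscheduled visits a code of their own, separate from that of Visit 1. The visit-adjustment text in 14.3 moves out-of-window data to a scheduled visit but does not say which of two pre-dose values is baseline. Re-screening is not a route to conflict: it opens a new eCRF and screening number, hence a new Visit 1.

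**4. Size of the numeric effect.** Let S be the Screening value, R the later pre-dose repeat and Y a post-dose value.

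- Change under the SAP: Y − S. Change under the protocol: Y − R.
- Error for that volunteer: (Y − S) − (Y − R) = R − S, at every post-dose visit.
- Error in the cohort mean with one such volunteer among n: (R − S)/n. For n = 3 this is 33% of R − S; for n = 6 it is 17%.

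**5. Effect on transition categories.** These are the SAP's own definitions, with the repeat taken as Normal. I assume that a pair in the same class counts as Unchanged. MH = medical history, AE = adverse event, CS = clinically significant, NCS = abnormal but not clinically significant.

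| Screening value | Post-dose value | Category from Screening | Category from repeat |
|---|---|---|---|
| NCS | Normal or NCS | Unchanged | Unchanged |
| NCS | CS (AE) | Worsened (AE) | Worsened (AE) |
| CS (MH) | Normal or NCS | Relieved | Unchanged |
| CS (MH) | CS (MH) | Unchanged | Worsened (MH) |
| CS (MH) | CS (AE) | Worsened (AE) | Worsened (AE) |
| CS (AE) | Normal or NCS | Relieved | Unchanged |
| CS (AE) | CS (AE) | Unchanged | Worsened (AE) |

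No category changes when the Screening value was abnormal but not clinically significant.

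**6. Frequency.** The documents give no re-test count. The possible range is 0 to all of the roughly 29 volunteers to be recruited. Because 6.1 limits re-tests to causes of screen failure, a low number is more plausible.

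**The case against.** The strongest reply is that the SAP applies the protocol's rule correctly to the schedule. It uses Day 1 pre-dose wherever a Day 1 value is planned and Screening where none is. That stands for every volunteer without a repeat.

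A second reply is that a re-test on Days -14 to -1 falls inside the Visit 1 window and might simply be recorded as Visit 1. That is possible. The SAP would still not say which of two Visit 1 values to use, so the gap narrows but does not close.

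A third is that inclusion criterion 4 requires clinically normal laboratory results in the investigator's judgement, so few enrolled volunteers should have a clinically significant first value. This limits the problem. However, a laboratory result that caused screen failure and was then repeated is the kind most likely to have been coded that way.

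Three stronger readings are tempting, and the documents do not support them:

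- **The SAP ignores an existing Day 1 laboratory value.** It does not. The Day 1 pre-dose draw is for PK, and that day's laboratory tests come 8 hours after the first dose.
- **Dose-limiting toxicity calls are affected.** Protocol 2.1 defines a DLT by grade, timing and investigator-judged relatedness. Section 8.1 makes a laboratory abnormality an adverse event on the investigator's judgement of clinical significance. Neither uses the SAP baseline.
- **Worsening is masked in general.** The table above shows that it is hidden only when the superseded value was itself clinically significant, and not in every such case.

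**Conclusion.** The point holds in a narrow, conditional form. The SAP replaces the protocol's timing rule with a fixed visit and does not declare this among its departures. The baseline differs only for a volunteer with a later pre-dose laboratory result that is not filed under Visit 1. For that volunteer the numeric change is off by R − S, and the cohort mean by one sixth to one third of that. The transition category can move only if the superseded value was clinically significant. The fractions assume one such volunteer in a cohort of 3 to 6. The laboratory tables use the ITT population, so n may be slightly larger and the fraction smaller. Frequency is unknown. Dose-escalation decisions and the primary endpoint are untouched.

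A separate matter is that the scheduled laboratory baseline can be up to two weeks old. It can also precede the diet restrictions that protocol 3.5 starts 24 hours before Day 1. This follows from the protocol's schedule and is not a SAP departure, and rewording the SAP will not change it.

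**What to change.** **SAP, wording only.** In the laboratory column of the 14.3 visit table and in both programmer's notes under 14.3.5, define laboratory and immunology baseline as the last non-missing value before the first dose, including repeat and unscheduled tests, and note that this will usually be Visit 1. The cost is a line of programming logic. Results change only for volunteers with a later pre-dose value. It would also help to state in the report that scheduled laboratory baselines precede dosing by 1 to 14 days.

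**Protocol, optional, only if dosing is not finished.** Add the routine laboratory and immunology panel to the fasted Day 1 pre-dose draw, as routine laboratory tests already accompany the PK draw on Days 2 to 5. The cost is about 29 extra panels and some additional blood volume. The baseline gap shortens to the day of dosing. The overlap of diet and drug remains, because the restrictions would have run for only about a day and continue to Day 7. The SAP is dated 08-SEP-2022 and expected the last subject to leave in March 2022, so this step probably comes too late for this trial.

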14.3.1 Treatment Emergent Adverse Event – Subject Based Analyses

For 14.3.1.4, population will include ITT and MTD-Evaluable population.

14.3.1.1 Treatment Emergent AE - Summary

Population: Intent-to-Treat Population / MTD-Evaluable Population

Characteristics [Event#:Subj#]	Treatment	
Repeat Population: Intent-to-Treat Population, MTD-	Evaluable Population	
n	XXX	
Subjects with AE	XXX : XXX (XXX.X%)	
Subjects with Treatment-Related AE	XXX : XXX (XXX.X%)	
Subjects with DLT	XXX : XXX (XXX.X%)	
Subjects with Grade ≥3 AE	XXX : XXX (XXX.X%)	
Subjects with Grade ≥3 Treatment-Related AE	XXX : XXX (XXX.X%)	
Subjects with AE Leading to Action Taken	XXX : XXX (XXX.X%)	
Subjects with AE Leading to Drug withdrawn	XXX : XXX (XXX.X%)	
Subjects with SAE	XXX : XXX (XXX.X%)	
Subjects with Death SAE	XXX : XXX (XXX.X%)	
Subjects with SUSAR	XXX : XXX (XXX.X%)	
Subjects with Death SUSAR	XXX: XXX (XXX.X%)	

Subject with multiple events are counted as one incidence.

Treatment-Related is defined as Definitely Related, Probable Related, or Possibly Related

Programmer's Notes:

Repeat Population only when the two populations are not identical

14.3.1.2 Treatment Emergent AE - Subjects with AE

14.3.1.3 Treatment Emergent AE - Subjects with Treatment-Related AE

14.3.1.4 Treatment Emergent AE – Subjects with DLT

[For 14.3.1.2-3] Population: Intent-to-Treat Population

[For 14.3.1.4] Population: Intent-to-Treat Population / MTD-Evaluable Population

Characteristics [Event#:Subj#]	Dose Level	
Repeat Population: Intent-to-Treat Population, MT	TD-Evaluable Population (Applied for	
14.3.1.4)		
. By MedDRA SOC and Preferred Term		
n	XXX	
At least one below	XXX : XXX (XXX.X%)	
<meddra 1="" body="" system=""></meddra>	XXX : XXX (XXX.X%)	
<meddra 1="" preferred="" term=""></meddra>	XXX : XXX (XXX.X%)	
<meddra 2="" preferred="" term=""></meddra>	XXX : XXX (XXX.X%)	
<meddra 3="" preferred="" term=""></meddra>	XXX : XXX (XXX.X%)	
	XXX : XXX (XXX.X%)	
<meddra 2="" body="" system=""></meddra>	XXX : XXX (XXX.X%)	
<meddra 1="" preferred="" term=""></meddra>	XXX : XXX (XXX.X%)	
<meddra 2="" preferred="" term=""></meddra>	XXX : XXX (XXX.X%)	
<meddra 3="" preferred="" term=""></meddra>	XXX : XXX (XXX.X%)	

For each MedDRA (version 23.0) SOC or Preferred Term, Subject with multiple events are counted as one incidence

[For 14.3.1.3] Treatment-Related is defined as Definitely Related, Probable Related, or Possibly Related

Programmer's Notes:

Repeat Population only when the two populations are not identical

Sorted in descending order of Subject No, Event No. of Total column by MedDRA Body System first, and then MedDRA Preferred Term.

Version 1.0, 08-SEP-2022 Confidential
Protocol No.: Careseng 1370-01 Page 13 of 20

Careseng 1370 for Healthy Volunteers

14.3.1.5 Treatment Emergent AE - Subjects with Grade ≥3 AE

14.3.1.6 Treatment Emergent AE - Subjects with Grade ≥3 Treatment-Related AE

Population: Intent-to-Treat Population

Characteristics [Event#:Subj#]	Dose Level
. By Severity Grade, MedDRA SOC and Preferred Term	
n	XXX
At least one below	XXX: XXX (XXX.X%)
Grade ≥3, Grade 4, Grade 5	XXX: XXX (XXX.X%)
<meddra 1="" body="" system=""></meddra>	XXX : XXX (XXX.X%)
<meddra 1="" preferred="" term=""></meddra>	XXX : XXX (XXX.X%)
<meddra 2="" preferred="" term=""></meddra>	XXX : XXX (XXX.X%)
<meddra 3="" preferred="" term=""></meddra>	XXX: XXX (XXX.X%)
	XXX: XXX (XXX.X%)
<meddra 2="" body="" system=""></meddra>	XXX: XXX (XXX.X%)
<meddra 1="" preferred="" term=""></meddra>	XXX : XXX (XXX.X%)
<meddra 2="" preferred="" term=""></meddra>	XXX : XXX (XXX.X%)
<meddra 3="" preferred="" term=""></meddra>	XXX:XXX(XXX.X%)

[For 14.3.1.6] Treatment Related is defined as Definitely Related, Probable Related, or Possibly Related

Programmer's Notes:

Sorted in descending order of Subject No, Event No. of Total column by MedDRA Body System first, and then MedDRA Preferred Term for each Grade Level

14.3.1.7 Treatment Emergent AE - Subjects with AE Leading to Action Taken

Population: Intent-to-Treat Population

r opulation. Intent to Treat r opulation	
Characteristics [Event#:Subj#]	Dose Level
. By Action Taken, MedDRA SOC and Preferred Term	
n	XXX
At least one below	XXX: XXX (XXX.X%)
Drug interrupted, Drug withdrawn	XXX:XXX(XXX.X%)
<meddra 1="" body="" system=""></meddra>	XXX : XXX (XXX.X%)
<meddra 1="" preferred="" term=""></meddra>	XXX : XXX (XXX.X%)
<meddra 2="" preferred="" term=""></meddra>	XXX : XXX (XXX.X%)
<meddra 3="" preferred="" term=""></meddra>	XXX: XXX (XXX.X%)
<meddra 2="" body="" system=""></meddra>	XXX : XXX (XXX.X%)
<meddra 1="" preferred="" term=""></meddra>	XXX : XXX (XXX.X%)
<meddra 2="" preferred="" term=""></meddra>	XXX : XXX (XXX.X%)
<meddra 3="" preferred="" term=""></meddra>	XXX : XXX (XXX.X%)

Programmer's Notes:

Sorted in descending order of Subject No, Event No. of Total column by Action Taken first, then MedDRA Body System, and then MedDRA Preferred Term

Version 1.0, 08-SEP-2022 Protocol No.: Careseng 1370-01

Careseng 1370 for Healthy Volunteers

14.3.1.8 Treatment Emergent AE – Subjects with SAE

14.3.1.9 Treatment Emergent AE – Subjects with SUSAR

SUSAR: Suspected Unexpected Serious Adverse Reaction (Unexpected **Treatment Related SAE)**

Population: Intent-to-Treat Population

Characteristics [Event#:Subj#]	Dose Level
. By SAE Criteria, MedDRA SOC and Preferred Term	
n	XXX
At least one below	XXX: XXX (XXX.X%)
<sae criterion=""></sae>	XXX : XXX (XXX.X%)
<meddra 1="" body="" system=""></meddra>	
<meddra 1="" preferred="" term=""></meddra>	XXX : XXX (XXX.X%)
<meddra 2="" preferred="" term=""></meddra>	XXX: XXX (XXX.X%)
<meddra 3="" preferred="" term=""></meddra>	XXX: XXX (XXX.X%)
	XXX : XXX (XXX.X%)
<meddra 2="" body="" system=""></meddra>	
<meddra 1="" preferred="" term=""></meddra>	XXX : XXX (XXX.X%)
<meddra 2="" preferred="" term=""></meddra>	XXX : XXX (XXX.X%)
<meddra 3="" preferred="" term=""></meddra>	XXX: XXX (XXX.X%)
	XXX:XXX(XXX.X%)

[figure not shown]
SAE Criteria 'F/L/H' and 'F/L' will be counted as 'F' only, and 'L/H' as 'L', where F=Fatal (Death), L=Life threatening, H=Require hospitalization or prolongation of existing hospitalization.

Programmer's Notes:

SAE Criterion: {Any SAE Criterion, Requires or Prolongs Hospitalization, death, ...}

Sorted in descending order of Subject No, Event No. of Total column by SAE Criterion, MedDRA Body System, and

MedDRA Preferred Term

Careseng 1370 for Healthy Volunteers

